## **VII. Potential benefits**

We do not expect any direct benefit to any subjects in this study. However, we hope that this study contributes important information for the development of joint kinematics analysis technique. An improved knowledge of carpal kinematics can inform future patients and surgeons and help optimize surgical techniques.

## **VIII. Monitoring and Quality Assurance**

The Principal Investigator, [name], has overall responsibility for monitoring and assuring the validity and integrity of the data and adherence to the IRB-approved protocol. All data acquired as specified by this protocol will be maintained and monitored by [name] and [REDACTED] at Bioengineering Laboratory. An IRB approved study staff will be responsible for collecting the signed consent forms and subject questionnaires. [REDACTED] will maintain the subject consent forms and questionnaires and review the forms for completeness. All electronic data and subject information will be secured on non-networking password protected computers; all paperwork will be secured in locked filing cabinets.

The Principal Investigator, [name], has overall responsibility for data and safety monitoring. A credentialed, Massachusetts licensed physician or a licensed radiological technologist will be operating fluoroscopes for this study. Subjects are monitored by [name] (or research fellows, approved as study staff) during the time of fluoroscopic image acquisition. Other study representatives will also be on hand to assist the subject. Participants will be supervised by the clinical technicians of the MGH Imaging Department during the MR acquisition. Any discomfort during fluoroscopy or MRI will lead to termination of the procedure and excluding the participants from the study.

The study staff will update the treating physicians on the imaging procedures. The treating physicians will decide whether the subject is eligible to continue his or her participation in the study.

The principal investigator will review, analyze, and report to the IRB any adverse events according to the guidelines set forth by MGH/Partners.

All participants are given a participation number/code at the time of enrollment. This code is kept on all data sheets instead of the subject name. Subject information is only accessible by Partners authorized investigators and will not be shared with outside entities.

Questionnaires and self-reported responses will not become part of the subject's medical record and will not contain medical record numbers or names. Hardcopies of study related data and forms will be stored in a lockable file cabinet. Subject information

will remain confidential by keeping identifying information (name, medical record number, and subject number) in a separate locked file cabinet. Only the investigators and study staff specified on the consent form will have access to this information.

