#### I. Background and Significance

The kinematics of scapholunate interosseous ligament (SLIL) injuries are poorly understood. Some patients are relatively asymptomatic while other patients have pain and difficulty with pushing and loading of the wrist. Even more confounding, some patients with complete injury and dissociation of the scaphoid from the lunate may be symptom free, while some patients with partial injuries describe substantial wrist dysfunction.

The kinematics of the wrist may provide insight into this dysfunction. *In vivo* kinematics of the normal wrist has been studied previously, but few studies have characterized the wrist with a SLIL injury. In addition, there are few studies evaluating validated patient-rated outcomes for patients with SLIL injury. The goal of this study would be to evaluate to what degree kinematic abnormalities affect patient-rated outcomes.

A dual fluoroscopic imaging technique has been used to study the kinematics of various joints and quantify the variations associated with ligament insufficiency or ligament reconstruction. We propose an *in-vivo* study on the wrist of patients with SLIL injury. This technique should identify any changes in carpal kinematics and may be able to be correlated to signs and symptoms of pain and osteoarthritis.

Our technique provides a direct technique for measurement of wrist kinematics. The system is not only a viable solution for the investigation of fully dynamic joint kinematics, but also has a low radiation dosage, is non-invasive, and can be constructed using any pair of readily available fluoroscopes. Thus, the DFIS provides an easy and powerful tool for accurately determining 6DOF positions of healthy, injured, and surgically treated wrists in 3D space.

- (1) Wolfe SW et al. *In vivo* scaphoid, lunate, and capitate kinematics in flexion and extension. *J Hand Surg Am* 2000; 25A : 860-9.
- (2) Crisco JJ et al. *In vivo* radiocarpal kinematics and the dart-thrower's motion. *J Bone Joint Surg* 2005; 87A: 2729- 2739.
- (3) Moritomo H et al. Capitate-based kinematics of the midcarpal joint during wrist radioulnar deviation: An *in vivo* three-dimensional motion analysis. *J Hand Surg* 2004; 29A: 668-675.
- (4) Li G et al. *In vivo* articular cartilage contact kinematics of the knee: an investigation using dual-orthogonal fluoroscopy and magnetic resonance image-based computer models. *Am J Sports Med.* 2005 Jan;33(1):102-7.

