## II. Specific aims

This represents a study on subjects with scapholunate interosseous ligament (SLIL) injury and *in-vivo* joint kinematics analysis based on a new three-dimensional imaging method which will integrate images from CT scan and from dual-orthogonal fluoroscopy.

We hypothesize that there is no relationship between *in vivo* kinematic abnormalities and patient-rated outcomes for scapholunate interosseous ligament injuries (SLIL)

Our secondary null hypotheses are that: There are no kinematic differences between subjects with unilateral, symptomatic, full thickness scapholunate ligament tears in comparison to the contralateral wrist without scapholunate ligament injury.

We also aim to answer to the below questions:

- What are baseline validated outcomes for subjects with SLIL injury?
- What are baseline physical measures (range of motion, Jamar Dynamometry)?

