## III. Subject selection

In this pilot study, we will recruit 10 subjects with the below inclusion criteria:

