### Inclusion Criteria

- Patients with a unilateral full thickness scapholunate ligament tear diagnosed by radiographs or advanced imaging.

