### **V.I. Study visits**

Subjects with a unilateral, full thickness scapholunate ligament tear documented by radiographs of the interest and contralateral wrist, MR arthrogram, or MRI of the interest wrist as well with no history or radiographic evidence of wrist injury will be enrolled. A CT scan of both wrists will be obtained. The contralateral wrist will serve as a matched control.

[figure not shown]
Participation in this study will require two visits at the Massachusetts General Hospital. A research assistant who is IRB approved study staff will contact the subject by telephone and/or email to schedule the visits and will ask the subject whether he/she would prefer to do the CT scan and Fluoroscopy in either one longer session or two separate shorter sessions.

The *first visit* after enrolling in this study will be to undergo a CT scan of both wrists. This visit will last approximately 60 minutes. The subject will lie motionless with outstretched hands on a table that slides into a square donut frame for about 2 minutes. Subjects will complete the PRWE, DASH, and SF-12 questionnaires. Questionnaires will be completed on paper. Range of motion of both wrists will be assessed using a goniometer. Grip force of both wrists will be assessed using Jamar Dynamometer. Pinch force will be assessed for both sides using pinch gauge.

The *second visit* will last approximately 60 minutes. Images of the both wrists will be taken with fluoroscopes, which are able to take digital x-ray pictures. During this visit, the subject will perform fully dynamic activities as described below, while the fluoroscopes take digital x-rays, one wrist at a time:

[REDACTED]

[REDACTED]

Each subject will be given a radiation protection apron, a protective thyroid shield, and protection for genital region. The first and second visits can be done in the same day or 2 separate days, whichever is more convenient for the subject.

The data obtained from these visits will be transferred to a computer and will be used to reconstruct three-dimensional wrist models. It will help researchers better understand the association of small bones in the wrist and whether any changes happen in their related movements after SLIL injury.

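### Discomfort during fluoroscopy removes the participant from the study as well as ending the imaging, so the rule as written can take out the more symptomatic subjects and their data

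*Combined protocol and SAP*

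**What the plan says.** The rule is in section VIII, Monitoring and Quality Assurance: "Any discomfort during fluoroscopy or MRI will lead to termination of the procedure and excluding the participants from the study". It has two consequences, ending the procedure and excluding the person. It does not grade discomfort, separate the injured from the control wrist, or separate one task from the whole study. The next paragraph leaves continued eligibility to the treating physicians.

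Fluoroscopy is the second study visit. Section V.I (Study visits) says "the subject will perform fully dynamic activities as described below, while the fluoroscopes take digital x-rays, one wrist at a time"; the list that follows is redacted. Section V.II (Devices to be used) adds imaging at the extremes of motion, and the Biostatistical Analysis section adds a gripping and a leaning position. PRWE, DASH, SF-12, range of motion, grip, pinch and CT all belong to the first visit.

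On size and population: "In this pilot study, we will recruit 10 subjects", and the inclusion criterion is "Patients with a unilateral full thickness scapholunate ligament tear diagnosed by radiographs or advanced imaging". Section I describes a wide range of symptoms: "Some patients are relatively asymptomatic" while "other patients have pain and difficulty with pushing and loading of the wrist". Section II asks whether kinematic abnormality relates to patient-rated outcome, whether the injured wrist differs from the other one, and "What are baseline validated outcomes for subjects with SLIL injury".

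**The concern.** The imaging asks subjects to do what the background section says hurts some of them, and discomfort while doing it is grounds for exclusion. Subjects who report discomfort are plausibly those with worse PRWE and DASH scores, and those scores are one side of the main hypothesis. Three things are at stake:

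- **Main hypothesis.** Fewer subjects and a narrower spread of outcomes both make a true relation harder to detect. The stated hypothesis is of no relation, so a null result would be harder to interpret.
- **Comparison with the other wrist.** Each excluded subject is a lost pair.
- **Baseline description.** If excluded subjects' visit 1 data are dropped, PRWE and DASH will look milder than they are among the people enrolled.

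**Working it through.** **1. The plan's own figure.** The sample size of 10 comes with no alpha, power, effect size or dropout allowance, so there is nothing to reproduce. Everything below is illustrative.

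**2. Chance of losing subjects.** The documents give no discomfort rate, so assume p per subject. P(at least one of 10 lost) = 1 − (1 − p)^10. At p = 10% this is 1 − 0.9^10 = 65%; at p = 30% it is 1 − 0.7^10 = 97%. The binomial chance of losing three or more is 7% and 62%.

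**3. Power for the main hypothesis.** The only method named is a possible logistic regression, so a two-sided 5% Pearson test stands in: t = r√((n−2)/(1−r²)) on n−2 degrees of freedom. The smallest significant r is t/√(n−2+t²): 0.63 at n = 10, 0.67 at n = 9 and 0.75 at n = 7.

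The simulation (200,000 trials) takes Y as PRWE, discomfort D = aY + √(1−a²)e₁ and kinematic abnormality X = ρY + √(1−ρ²)e₂, and drops the k subjects of 10 with the highest D. Central a is 0.6, range 0.3 to 0.8; a = 0 is random loss. Power, %:

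| True ρ | All 10 | 1 lost at random | 1 lost on discomfort | 3 lost at random | 3 lost on discomfort |
|---|---|---|---|---|---|
| 0.3 | 13.3 | 11.9 | 11.4 (11.9 to 10.9) | 9.8 | 8.9 (9.5 to 8.3) |
| 0.6 | 48.5 | 43.1 | 40.4 (42.4 to 38.1) | 31.2 | 27.3 (30.4 to 23.9) |
| 0.8 | 86.8 | 81.9 | 79.5 (81.4 to 77.1) | 66.9 | 60.4 (65.4 to 54.5) |

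At ρ = 0.6 with three lost, the fall is 48.5 − 27.3 = 21.2 points. Smaller n accounts for 48.5 − 31.2 = 17.3 of these and selection for 31.2 − 27.3 = 3.9.

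**4. Paired comparison of wrists.** The smallest standardised difference d with 80% power solves P(T > t₀.₉₇₅) = 0.80, where T is noncentral t with m−1 degrees of freedom and noncentrality d√m. It is 1.00 SD of the differences for 10 pairs, 1.07 for 9 and 1.27 for 7.

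**5. Baseline means, if visit 1 data are dropped.** In the same simulation mean PRWE shifts towards milder by 0.10 SD (0.05 to 0.14) with one lost and 0.27 SD (0.14 to 0.36) with three lost. The standard errors are 1/√9 = 0.33 SD and 1/√7 = 0.38 SD, so both shifts are smaller than the sampling error.

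**6. Rule against fix.** Steps 3 and 4 compare the rule with complete data on all 10, but a fix that keeps the safety stop does not deliver that. Take three subjects stopped at one loaded position:

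- At a position all 10 completed earlier, n is 10 under the fix and 7 under the rule if it drops their data. The whole 21 points are then recoverable at ρ = 0.6.
- At the position where they stopped, n is 7 either way and the selection is the same. Nothing is recovered.
- If the rule in practice keeps data already collected, the fix adds nothing to those analyses beyond making the retention explicit.

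The figures in steps 3 and 4 are therefore upper bounds. The share recovered depends on the order of tasks and wrists, which is not visible.

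**The case against.** A conservative stop is defensible in a study with no expected direct benefit. The sentence reads like a general imaging-tolerance clause: it treats fluoroscopy and MRI together, although MRI appears elsewhere as routine diagnosis. The treating physicians have a say on continuation. The redacted task list may set the order or limit tasks by pain, and consent pages, which may cover retention of data, are not available. Enrolment can be extended with IRB approval. The study is a pilot with only about 48% power at ρ = 0.6 even with nobody lost.

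Much of this stands. The safety stop should remain, the intent may be milder than the wording, and frequency cannot be judged. Selection itself is a small effect. Other parts do not remove the point. The physician sentence does not withdraw the automatic exclusion, so the two are at best in tension. Excluding someone after the procedure has stopped adds no protection. The enrolment extension is tied to the size of the regression model and is not a replacement rule. Replacement would also leave the selection in place: at ρ = 0.6 and a = 0.6, with n restored to 10, power is 45% with 10% excluded and 42% with 30% excluded.

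A reader might also infer that the plan deletes usable data. The text excludes the participant and does not say what happens to data already collected.

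**Conclusion.** The point holds as one about an explicit rule. Followed as written, it can remove subjects with worse symptoms from a study of patient-rated outcomes, and their visit 1 outcomes and completed positions may go with them. The change is worth making because it is cheap and each subject is a tenth of the data.

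The size is uncertain. Under assumed correlations of 0.6 and 0.6, losing one to three whole subjects takes power from about 48% to about 40% or 27%. This is mostly smaller n, is an upper bound on what the fix recovers, and does not apply at the position where a subject stopped. At a true correlation of 0.3 power is low throughout and little changes.

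Two stronger readings are not supported. One is that the rule demonstrably selects on the outcome: the link between imaging discomfort and PRWE or DASH is plausible from the background section, but no data on it are given. The other is that the fall to 27% is the price of the rule: that needs three exclusions and loss of all their data, and the documents establish neither.

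**What to change.** Reword the sentence in section VIII so that:

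- discomfort ends the task or the session, and the subject stays in the study unless consent is withdrawn or the treating physician advises otherwise;
- visit 1 data are kept and used for the baseline aims, and every position already imaged in either wrist is kept for the kinematic analyses;
- the position, wrist and reason for stopping are recorded, and the number stopped is reported with their PRWE and DASH scores;
- each position is analysed among those who completed it, and the report says whether subjects with no usable fluoroscopy are replaced.

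If the redacted list does not already do so, image gripping and leaning last, so that a stop there costs no other position.

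The cost is one or two sentences in an IRB amendment and one stop-reason field on the visit 2 form, with no added visits, imaging or radiation. The gain is the visit 1 data and the positions completed before the stop. The downside is that n will differ by position. A paired comparison at a position also needs both wrists imaged there. The loaded positions stay selected on pain, which should be stated as a limitation.
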